3.4.10 Physical Examinations

A symptom-directed physical examination, including height and weight, will be performed at scheduled time points as indicated in the Schedule of Events ([Table 9](#), [Table 11](#), and [Table 12](#)). The physical examination may include assessment of skin, head, ears, eyes, nose, throat, neck, thyroid, lungs, heart, cardiovascular, abdomen, lymph nodes, and musculoskeletal system/extremities. Any clinically significant finding identified during a study visit should be reported as a MAAE.

Symptom-directed physical examinations may be performed at other timepoints at the discretion of the investigator. On each injection day before injection and again 7 days after injection, the arm receiving the injection should be examined and the associated lymph nodes should be evaluated.

Body mass index will be calculated at the Screening Visit (Day 0) only.

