If participants are confirmed to have SARS-CoV-2 infection, and are asymptomatic, the investigator will notify the participant's primary care physician and local health authority, as per local regulations. If the participant had known exposure to COVID-19 (eg, exposure to someone with confirmed COVID-19 disease), it will be captured in the COVID-19 exposure form, and the participant will be discontinued from future study treatment only, and will continue to follow all other study assessments as outlined in the protocol. Additionally, a convalescent visit will be scheduled approximately 28 days after diagnosis. At this visit, a blood sample will be collected for potential immunologic assessment of SARS-CoV-2 infection.

Any confirmed SARS-CoV-2 infection occurring in participants, except asymptomatic infection diagnosed at Day 1, will be captured as an MAAE along with relevant concomitant medications and details about severity, seriousness, and outcome.

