3.4.8.2 Medically Attended Adverse Event

An MAAE is an AE that leads to an unscheduled visit to a healthcare practitioner (HCP). This would include visits to a study site for unscheduled assessments (eg, rash assessment, abnormal laboratory follow-up, SARS-CoV-2 infection [[Section 3.4.1](#)]) and visits to HCPs external to the study site (eg, urgent care, primary care physician). Investigators will review unsolicited AEs for the occurrence of any MAAEs. All MAAEs must be fully reported on the MAAE page of the eCRF.

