4.3 Analysis Endpoints

4.3.1 Part A, Blinded

4.3.1.1 Primary Endpoints

4.3.1.1.1 Primary Safety Endpoints

The primary safety objective will be evaluated by the following safety endpoints:

- Solicited local and systemic ARs through 7 days after each injection.
- Unsolicited AEs through 28 days after each injection.
- MAAEs through the entire study period.
- SAEs throughout the entire study period.
- Safety laboratory abnormalities at Day 29 and Day 57 (Cohort 2 only).
- Vital sign measurements and physical examination findings.

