7. Physical examination: A full physical examination, including height and weight, will be performed at Day 1, Day 29, and Day 57. Symptom-directed physical examinations may be performed at other time points at the discretion of the investigator. On each injection day before injection and again 7 days after injection, the arm receiving the injection should be examined and the associated lymph nodes should be evaluated. Any clinically significant finding identified during a study visit should be reported as an MAAE. Vital signs are to be collected pre- and post-dosing on days of injection (Day 1 and Day 29). When applicable, vital sign measurements should be performed before blood collection. Participants who are febrile (body temperature $\geq 38.0^{\circ}\text{C}/100.4^{\circ}\text{F}$) before injection on Day 1 or Day 29 must be rescheduled within the relevant window period to receive the injection. Afebrile participants with minor illnesses can be administered investigational product at the discretion of the investigator.
8. Pregnancy test at Screening and Day 1 and before the second study injection will be a point-of-care urine test. At the discretion of the investigator a pregnancy test either via blood or point-of-care urine test can be performed. Follicle-stimulating hormone level may be measured to confirm menopausal status at the discretion of the investigator.
9. Sample must be collected prior to dosing on days of injection (Day 1 and Day 29).
10. The nasopharyngeal swab sample, collected prior to vaccination on days of injection (Day 1 and Day 29), will be used to ascertain the presence of SARS-CoV-2 via PCR.
11. Diary entries will be recorded by the participant starting approximately 1 hour after injection while at the study site with instruction provided by study staff. Study participants will continue to record in the eDiary each day after they leave the study site, preferably in the evening and at the same time each day, on the day of injection and for 6 days following injection. Any solicited AR that is ongoing beyond Day 7 will be reported in the eDiary until resolution. Adverse reactions recorded in eDiaries beyond Day 7 should be reviewed either during the next telephone call or at the next study site visit.

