Note: In accordance with “FDA Guidance on Conduct of Clinical Trials of Medical Products during COVID-19 Public Health Emergency” (DHHS 2020), investigators may convert study site visits to telemedicine visits with the approval of the Sponsor.

1. The Participant Decision Visit is only applicable to Part B and may be performed over multiple visits if within the given window.
2. Participants who received 1 dose of mRNA-1273 (50 or 100ug) in Part A and agree to receive 1 dose of mRNA-1273 in Part B, will follow [Table 11](#) Schedule of Events.
3. Safety follow-up via eDiary questionnaire will be performed every 4 weeks starting at OL-Day 71 to OL-Day 155. These study days are relative to OL-Day 1 vaccine administration.
4. Physical examination: A symptom-directed physical examination, including height and weight, will be performed at OL-Day 1, OL-Day 29, and OL-Day 57. Symptom-directed physical examinations may be performed at other time points at the discretion of the investigator. On the day of injection before injection and again 7 days after injection, the arm receiving the injection should be examined and the associated lymph nodes should be evaluated. Any clinically significant finding identified during a study visit should be reported as an MAAE. Vital signs are to be collected pre- and post-dosing on days of injection (OL-Day 1). When applicable, vital sign measurements should be performed before blood collection. Participants who are febrile (body

temperature $\geq 38.0^{\circ}\text{C}/100.4^{\circ}\text{F}$) before injection on OL-Day 1 must be rescheduled within the relevant window period to receive the injection. Afebrile participants with minor illnesses can be administered investigational product at the discretion of the investigator.

5. Sample must be collected prior to dosing on days of injection.
6. The nasopharyngeal swab sample, collected prior to vaccination on days of injection, will be used to ascertain the presence of SARS-CoV-2 via PCR.

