6.3.1. Adverse Events

A treatment-emergent AE (TEAE) is defined as any event not present before exposure to study vaccine or any event already present that worsens after exposure to study vaccine. [Note: worsening of a pre-existing condition after vaccination will be reported as a new AE.]

Adverse events will also be evaluated by the investigator for the coexistence of MAAE which is defined as an AE that leads to an unscheduled visit to a healthcare practitioner.

Unsolicited AEs will be coded by PT and SOC using MedDRA and summarized by age cohort, vaccination group, and stage (28 days after any vaccination stage for Part A and Part B separately, and Day1 to End of Study; see [Section 6.1](#) for definitions of vaccination group and stage).

All summary tables (except for the overall summary of AEs) for unsolicited AEs will be presented by SOC and PT for TEAEs with counts of subjects included. SOC will be displayed in internationally agreed order. PT will be displayed in descending order of frequency of total mRNA-1273 and then alphabetically within SOC. When summarizing the number and percentage of subjects with an event, subjects with multiple occurrences of the same AE or a continuing AE will be counted once. Subjects will be presented

according to the highest severity (the strongest relationship) in the summaries by severity (of related AEs), if subjects reported multiple events under the same SOC and/or PT.

Percentages will be based upon the number of subjects in the Safety Set within each vaccination group.

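### Sites must report any clinically significant study-visit finding as an MAAE, so the MAAE tables can count events outside the SAP's own unscheduled-visit definition of this primary safety endpoint

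*Protocol*

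**What the plan says.** **Definition.** Protocol 3.4.8.2 states: "An MAAE is an AE that leads to an unscheduled visit to a healthcare practitioner (HCP". It counts visits to the site for unscheduled assessments as well as visits to outside practitioners. SAP 6.3.1 (Parts A and B) repeats only this: "MAAE which is defined as an AE that leads to an unscheduled visit to a healthcare practitioner". Section 6.3.1 of the Part C SAP uses the same definition.

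**Reporting instruction.** Protocol 3.4.10 says that symptom-directed examinations "will be performed at scheduled time points as indicated in the Schedule of Events", and then: "Any clinically significant finding identified during a study visit should be reported as a MAAE". It sets no condition that an unscheduled visit took place. Footnote 7 of Table 9, footnote 3 of Table 11 and footnote 4 of Table 12 carry the same rule: "Any clinically significant finding identified during a study visit should be reported as an MAAE".

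**Use.** Protocol 4.3.1.1.1 lists "MAAEs through the entire study period" among the primary safety endpoints of Part A, and 4.3.2.1.1 and 4.3.3.1.1 do the same for Parts B and C. In both SAPs, Sections 6.3.1.1 and 6.3.1.2 tabulate subjects with medically attended unsolicited TEAEs, overall and by system organ class and preferred term.

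**The concern.** The definition asks whether an event made someone seek unscheduled care. The instruction asks only whether the investigator saw something clinically significant at a visit. A finding at a routine visit that leads nowhere further is an MAAE under the second and not under the first.

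The recording rules do not settle it. Protocol 3.4.8.2 sends MAAEs to an MAAE page of the eCRF, while 3.4.8.7 sends examination findings classed as AEs to the AE page. Two sites could record the same finding differently and both be following the protocol.

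The study tests no hypothesis (Protocol 4.2), so the descriptive proportion is itself the result. If two kinds of event are pooled, it is no longer the proportion of participants whose AE led to unscheduled care, which is how the SAPs define it.

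**Working it through.** No stated figure in the plan depends on this point, so the check is mainly a comparison of the two rules.

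**Step 1: where the rules differ.**

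| Situation | 3.4.8.2 and both SAPs | 3.4.10 and schedule footnotes |
|---|---|---|
| AE leads to a visit to an outside practitioner | MAAE | Not addressed |
| Significant finding at an unscheduled site assessment of an AE | MAAE | MAAE |
| Significant finding (an AE) at a scheduled visit, unscheduled visit follows | MAAE | MAAE |
| Significant finding at a scheduled visit, no unscheduled visit | Not an MAAE | MAAE |

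Only the last row is in conflict. Scheduled visits are clearly covered, because 3.4.10 concerns examinations at scheduled time points and the rule is repeated in three schedule footnotes.

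**Step 2: does the analysis remove the last row?** The SAP tables are limited to unsolicited TEAEs. That takes out solicited reactions and conditions that were present before vaccination and did not worsen. It does not take out a new finding at, say, Day 57 that led to no unscheduled visit. SAP 6.3.1 leaves MAAE status to the investigator, who works from the protocol. Neither SAP gives a derivation from visit data or a flag for source.

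**Step 3: can the size be computed?** Let m be the probability of an MAAE under the unscheduled-visit definition, q the probability of a reportable finding per examination, and k the number of examinations after the first injection day, all taken as independent. Then

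P(at least one MAAE) = 1 − (1 − m)(1 − q)^k.

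The documents give neither m nor q. Even k is uncertain. In Part A, footnote 7 of Table 9 requires a full examination on Days 1, 29 and 57, so k = 2 after Day 1. The combined examination and vital-signs row is marked at 8 visits after Day 1. With m = 10% assumed:

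- q = 0.25%, k = 2: 1 − 0.90 × 0.9975² = 10.4%; k = 8: 11.8%.
- q = 2%, k = 2: 1 − 0.90 × 0.98² = 13.6%; k = 8: 23.4%.

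The excess over 10% runs from 0.4 to 13.4 percentage points. At q = 2% and k = 8, m = 5% gives 19.2% (excess 14.2) and m = 20% gives 31.9% (excess 11.9). These are illustrations from assumed inputs. They show that the documents do not fix the size, and none of them is an estimate.

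For scale only, one reclassified participant moves the proportion by 1/100 = 1 point in a planned Part A cohort-by-dose cell and by 1/20 = 5 points in a planned Part C arm. That is true of any single event.

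**The case against.** The strongest reply is that there is only one analysis definition. Both SAPs state the unscheduled-visit definition, and Section 1 of each says the SAP prevails where its methods differ from the protocol's. On that view 3.4.10 is a cautious instruction to sites and has no bearing on the tables. In addition, the randomised Part A arms follow one schedule under observer-blind assessment, the parts are presented separately, and no test is planned.

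Much of this stands. Nothing here builds in a difference between Part A arms. A comparison of cumulative MAAE proportions across parts is not planned, and would be confounded anyway by follow-up to Day 394 in one case and OL-Month 6 or 7 in the others.

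The precedence clause does not close the gap, however. A definition can be applied only if the data show which events meet it, and the SAPs name no variable or rule for doing so. The eCRF is not among the documents. If it already records whether an unscheduled visit occurred, the remedy shrinks to a derivation rule in each SAP.

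**Conclusion.** The conflict holds and neither SAP resolves it. As written, the MAAE tables can include events that do not meet the SAPs' own definition of a primary safety endpoint. The size cannot be computed from the documents. The conclusion assumes that sites follow 3.4.10 and the footnotes and that MAAE status reaches the tables as the investigator recorded it.

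Two stronger readings are tempting and should not be drawn.

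- A reader counting marks in the examination rows (nine from Day 1 onward in Table 9, four each in Tables 11 and 12) might infer that Part A offers more than twice as many chances of such an MAAE. The row also covers vital signs. The footnotes name the same three examination days in every schedule: Days 1, 29 and 57, or their open-label equivalents. Part A visits also stop on entry to Part B.
- Protocol 3.4.1 says that confirmed infection, "except asymptomatic infection diagnosed at Day 1, will be captured as an MAAE". The open-label schedules describe "The nasopharyngeal swab sample, collected prior to vaccination on days of injection". A reader might infer that infections already present at OL-Day 1 inflate the Part B and Part C MAAE tables, and that the exemption should be widened. But those tables are limited to TEAEs, which by definition were not present before exposure or worsened after it, and 3.4.8.7 analyses AEs before vaccine receipt separately. Widening the exemption would also drop from MAAE capture infections that arose after Part A vaccination in Part B booster recipients.

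**What to change.** 1. Reconcile Protocol 3.4.8.2, 3.4.10, the footnotes to Tables 9, 11 and 12, and Section 6.3.1 of both SAPs, so that one definition governs.
2. Keep collecting every clinically significant finding. Table 9 stops scheduled recording of unsolicited AEs at Day 57 while MAAE recording runs to Day 394, so a narrower definition must not cause later findings to go unrecorded.
3. Record for each event whether an unscheduled visit to a practitioner or the site occurred.
4. Base the MAAE table on the 3.4.8.2 and SAP definition, and show findings from scheduled visits on a separate line, in the final Part B and Part C analyses.
5. For Part A, whose Day 57 report and end-of-part addendum are final (SAP Section 1), add a footnote or supplementary table stating what was counted. New protocol wording cannot change how those data were collected.

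The cost is some wording, one flag, one table line and a small recoding of existing records. No safety data are lost.

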4 STATISTICAL ANALYSIS PLAN

This section summarizes the planned statistical analysis strategy and procedures for the study. The details of statistical analysis will be provided in the statistical analysis plan (SAP), which will be finalized before the clinical database lock for the study and treatment unblinding. If, after the study has begun, but prior to any unblinding, changes are made to primary and/or key secondary objectives/hypotheses, or the statistical methods related to those hypotheses, then the protocol will be amended (consistent with ICH Guideline E9). Changes to other secondary or exploratory analyses made after the protocol has been finalized, along with an explanation as to when and why they occurred, will be listed in the SAP or CSR for the study. Ad hoc exploratory analyses, if any, will be clearly identified in the CSR.

4.1 Blinding and Responsibility for Analyses

Blinding during the Part A of the study will be managed as described in [Section 3.3.5](#). The Sponsor Biostatistics department or designee will generate the randomized allocation schedule(s) for study treatment assignment. Randomization will be implemented via an IRT.

Details regarding unblinded SMC review are described in [Section 6.1](#).

A limited number of Sponsor and CRO personnel will be unblinded to perform the primary analysis and prepare a final CSR after participants have completed Day 57 visit study procedures in Part A ([Section 3.3.5](#)). This primary analysis may be performed when all participants in Cohort 1 and the Cohort 2 sentinel group have completed Day 57 study procedures and/or when all participants in Cohort 1 and Cohort 2 have completed Day 57 study procedures. The study site staff, investigators, study monitors, and participants will remain blinded until the initiation of Part B.

Planned study analyses and data presentation for unblinded SMC review are described in [Section 4.7](#) and [Section 6.1](#), respectively. At each analysis, pre-identified Sponsor members will be unblinded to review treatment level results as defined in the study Data Blinding Plan. Unblinded data presentation or analysis for SMC review will be handled by the CRO unblinded team of statisticians and programmers, who are not involved in study design. A strict firewall between the CRO blinded and unblinded teams will be maintained during study conduct. Sponsor personnel who have access to review unblinded results will be documented. Sponsor and CRO personnel involved in the ongoing review and oversight of safety and immunogenicity will remain blinded until the initiation of Part B, as will study investigators and personnel at the study sites. The results of the primary analysis will not be shared with the investigators before completion of Part A of the study.

Part B and Part C will be open label.

4.2 Hypothesis Testing

There is no hypothesis testing in this study.

4.3 Analysis Endpoints

4.3.1 Part A, Blinded

4.3.1.1 Primary Endpoints

4.3.1.1.1 Primary Safety Endpoints

The primary safety objective will be evaluated by the following safety endpoints:

- Solicited local and systemic ARs through 7 days after each injection.
- Unsolicited AEs through 28 days after each injection.
- MAAEs through the entire study period.
- SAEs throughout the entire study period.
- Safety laboratory abnormalities at Day 29 and Day 57 (Cohort 2 only).
- Vital sign measurements and physical examination findings.

4.3.1.1.2 Primary Immunogenicity Endpoint

- Level of SARS-CoV-2-specific bAb measured by ELISA on Day 1, Day 29 (Month 1), Day 43, Day 57 (Month 2), Day 209 (Month 7), and Day 394 (Month 13), as applicable.

[figure not shown]
4.3.1.2 Secondary Endpoints

The secondary objective will be evaluated by the following endpoints:

- Titer of SARS-CoV-2-specific nAb on Day 1, Day 29 (Month 1), Day 43, Day 57 (Month 2), Day 209 (Month 7), and Day 394 (Month 13), as applicable.
- Seroconversion on Day 29 (Month 1), Day 43, Day 57 (Month 2), Day 209 (Month 7), and Day 394 (Month 13), as applicable.

4.3.1.3 Exploratory Endpoints

The exploratory endpoints are the following:

4.3.2 Part B, Open Label

4.3.2.1 Primary Endpoints (Part B, Open Label)

4.3.2.1.1 Primary Safety Endpoints

The primary safety objective will be evaluated by the following safety endpoints:

- Solicited local and systemic ARs through 7 days after each injection.
- Unsolicited AEs through 28 days after each injection.
- MAAEs through the entire study period.
- SAEs throughout the entire study period.
- Vital sign measurements and physical examination findings.

4.3.2.1.2 Primary Immunogenicity Endpoint

- For participants receiving 100 μ g of mRNA-1273 as 2 doses 28 days apart: Level of SARS-CoV-2-specific bAb measured by ELISA on OL-Day 1, OL-Day 8, OL-Day 15, OL-Day 29 (OL-Month 1), OL-Day 57 (OL-Month 2), and OL-Day 209 (OL-Month 7).
- For participants receiving 50 μ g of mRNA-1273 as a single booster: Level of SARS-CoV-2-specific bAb measured by ELISA on OL-Day 1, OL-Day 8, OL-Day 15, OL-Day 29 (OL-Month 1), OL-Day 57 (OL-Month 2), and OL-Day 181 (OL-Month 6).

[figure not shown]
4.3.2.2 Secondary Endpoints (Part B, Open Label)

The secondary objective will be evaluated by the following endpoints:

- For participants receiving 100 μ g of mRNA-1273 as 2 doses 28 days apart: Titer of SARS-CoV-2-specific nAb on OL- Day 1, OL-Day 8, OL- Day 15, OL- Day 29 (OL-Month 1), OL- Day 57 (OL-Month 2), and OL- Day 209 (OL-Month 7).
- For participants receiving 50 μ g of mRNA-1273 as a single booster: Titer of SARS-CoV-2-specific nAb on OL-Day 1, OL-Day 8, OL-Day 15, OL-Day 29 (OL-Month 1), OL-Day 57 (OL-Month 2), and OL-Day 181 (OL-Month 6).
- For participants receiving 100 μ g of mRNA-1273 as 2 doses 28 days apart: Seroconversion on OL-Day 8, OL-Day 15, OL-Day 29 (OL-Month 1), OL-Day 57 (OL-Month 2), and OL-Day 209 (OL-Month 7).
- For participants receiving 50 μ g of mRNA-1273 as a single booster: Seroconversion on OL-Day 8, OL-Day 15, OL-Day 29 (OL-Month 1), OL-Day 57 (OL-Month 2), and OL-Day 181 (OL-Month 6), and the proportion of participants with a ≥ 2 -, ≥ 3 -, or ≥ 4 -fold rise in antibody titer from open-label baseline.

4.3.2.3 Exploratory Endpoints (Part B, Open Label)

The exploratory endpoints are the following:

A large rectangular area of the page is completely blacked out, indicating that the content has been redacted.

4.3.3 Part C, Open Label

4.3.3.1 Primary Endpoints (Part C, Open Label)

4.3.3.1.1 Primary Safety Endpoints

The primary safety objective will be evaluated by the following safety endpoints:

- Solicited local and systemic ARs through 7 days after injection.
- Unsolicited AEs through 28 days after injection.
- MAAEs through the entire study period.
- SAEs throughout the entire study period.
- Vital sign measurements and physical examination findings.

